#### **12.4.2 Recording Adverse Events**

Throughout the study, the investigator at the site will record adverse events and serious adverse events as described previously (Section 12.2, Definitions) on the appropriate AE/SAE eCRF regardless of the relationship to study procedure.

Once recorded, an AE/SAE will be followed until it resolves with or without sequelae, or until the end of study participation, or until 30 days after the subject prematurely withdraws (without withdrawing consent)/or is withdrawn from the study, whichever occurs first.

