### **8.6 Final Study Visit**

A final study visit will be performed for all participants who began study treatment, regardless of whether or not they entered or completed the 24 week treatment course. The final visit will include:

- Final physical exam
- Blood draw
- Spirometry
- Pregnancy test (females only)

Participants recording only mild or no symptoms at the last office visit will be discharged from the study. Participants recording moderate or severe symptoms at the last office visit will require follow-up as described in 12, Safety Monitoring and Reporting.

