### **8.7 Early Termination Visit**

Participants may withdraw or be dropped from the study during or between study visits, according to the criteria in Section 11.2, Participant Stopping Rules and Withdrawal Criteria. For participants who withdraw or are dropped during a study visit, the visit will be terminated. The study clinician will perform a final clinical assessment, including blood collection and a targeted physical exam, as described in Section 8.6.

Participants who withdraw or are dropped from the study between visits will be contacted by phone and will be invited to the study center for a final assessment as described in Section 8.6 above. For participants who refuse to come to the clinic, the final clinical assessment as described above may be conducted over the phone. Besides this visit, no further follow-up will be made, except for participants who are discontinued due to pregnancy or SAEs. These participants will be contacted to determine the outcome of the pregnancy or the SAE. Refer to Section 12.6, Pregnancy Reporting, for more information on AE reporting for pregnancy.

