## **11 Criteria for Participant and Study Completion and Premature Study Termination**

### **11.1 Participant Completion**

The participants are considered to have completed the study once they have completed the Final Study Visit.

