**12.4 Collection and Recording of Adverse Events**

Adverse events (including SAEs) will be collected from the time of consent until a subject completes study participation or until 30 days after he/she prematurely withdraws (without withdrawing consent) or is withdrawn from the study.

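### Section 8.6 promises follow-up for participants still symptomatic at the last visit, but for completers Section 12 ends follow-up and AE collection at that same visit

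*Combined protocol and SAP*

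**What the plan says.** Section 8.6 divides participants by their symptoms at the last visit. For one group, "Participants recording only mild or no symptoms at the last office visit will be discharged from the study". For the other, "Participants recording moderate or severe symptoms at the last office visit will require follow-up as described in 12, Safety Monitoring and Reporting".

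Section 12 sets the duration of follow-up in 12.4.2: "an AE/SAE will be followed until it resolves with or without sequelae, or until the end of study participation", with a third limit of 30 days after premature withdrawal. The earliest limit governs; the sentence ends "is withdrawn from the study, whichever occurs first". The rule covers AEs and SAEs alike.

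Section 11.1 fixes when participation is complete: "The participants are considered to have completed the study once they have completed the Final Study Visit". It makes no exception for a participant with an open event.

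Section 12.4 sets the collection window for new events. They "will be collected from the time of consent until a subject completes study participation or until 30 days after he/she prematurely withdraws" or is withdrawn.

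Section 8.7, on early termination, says of the final assessment: "Besides this visit, no further follow-up will be made, except for participants who are discontinued due to pregnancy or SAEs". Those excepted participants are contacted to learn the outcome.

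**The concern.** Section 8.6 recognises that some participants will leave the last visit with symptoms that need following, and relies on Section 12 to say how. For someone who has completed treatment, Section 12 gives no period after that visit, so the cross-reference leads nowhere.

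This matters because safety is the primary objective, and the primary endpoint (3.2, 13.2.1) is the number of AEs and SAEs with their severity, seriousness and relatedness. Section 13.6 concedes that the sample is too small for a definitive assessment, so each event carries weight. Three things could be lost for completers: the outcome of an event open at the Final Visit, any later rise in its grade or change to serious, and any event that starts afterwards. Sites could also handle the same situation differently, since one could follow 8.6 and another 12.4.2 and both would be within the protocol.

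**Working it through.** No figure in the plan enters this point, so there is nothing to recompute. The check is to trace the cross-references and then look for any rule that fills the gap.

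**Tracing the rule for a completer.**
1. Section 8.6: moderate or severe symptoms at the last visit call for follow-up under Section 12.
2. Section 12.4.2: follow-up runs to the earliest of resolution, end of participation, or 30 days after premature withdrawal. The third limit does not apply to a completer.
3. Section 12.4.2 does not name the Final Study Visit. The link comes from 11.1, which puts completion there.
4. If the event is unresolved at the Final Visit, the earliest limit is that visit. Required follow-up afterwards: 0 days.
5. Section 12.4 ends collection of new AEs at the same point.

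**The groups side by side, as written.**

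| Participant | New AEs collected until | Open AE/SAE followed until |
|---|---|---|
| Completer (11.1, 12.4, 12.4.2) | Final Study Visit | Resolution or Final Study Visit, whichever is earlier |
| Premature withdrawal (12.4, 12.4.2) | 30 days after withdrawal | Resolution or 30 days after withdrawal; but 8.7 says nothing beyond the final assessment |
| Discontinued because of an SAE (12.4, 12.4.2, 8.7) | 30 days after withdrawal | As above, plus contact for the SAE outcome, with no time limit stated |

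The second row contains a further conflict. Sections 12.4 and 12.4.2 give withdrawals 30 days, while 8.7 allows them no follow-up after the final assessment unless they stopped for pregnancy or an SAE.

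**Looking for a rule elsewhere that covers completers.**
- Section 8.7: the outcome contact is limited to those discontinued for pregnancy or SAEs.
- Section 8.9: unscheduled visits are permitted for moderate to severe symptoms, with no duty to follow and no period after completion.
- Section 11.4: applies to withdrawals only, and points to 6.5, which adds a final blood sample.
- Section 12.2.4: deaths learned of in the follow-up period must be reported, but no such period is defined for completers.
- Section 12.5.1: the SAE form is updated when further details arrive; nobody is required to seek them.
- Section 12.6: follow-up to conclusion is for pregnancies only.

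None of these supplies the missing duty.

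**How many participants.** The 8.6 against 12.4.2 conflict applies only to completers with a moderate, severe or serious event open at the Final Visit. The documents give no rate for this. The end of new-AE collection applies to every completer, at most the 10–12 enrolled under 3.1.

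**The case against.** The best counter-reading is that 8.6 discharges only participants with mild symptoms or none. The others are then not yet discharged and still participating, so 12.4.2 keeps running. The wording helps a little, because 11.1 speaks of completing the study and 12.4.2 of the end of participation. The sentence in 12.4.2 also looks loosely drafted: read just as strictly for withdrawals, participation could be said to end at withdrawal and the 30-day clause would be empty. This reading is coherent, but no passage states it, 11.1 makes no such exception, and it leaves follow-up with no stated end for an event that does not resolve. If it is the intention, it needs writing down.

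For SAEs, the form can be updated without a cut-off (12.5.1), and the Medical Monitor decides the disposition of SAE reports (12.8.1). This stands, and a later outcome could be recorded. It is still not a duty to obtain one.

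Stopping collection of new AEs at the last visit is, taken alone, a design choice rather than a contradiction. That also stands.

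A reader might go further in four ways that the documents do not support.
- *That a reaction to the last injection has no collection window.* Section 8.4 requires at least 30 minutes' observation and a symptom questionnaire after each injection, 8.5.2 asks for immediate reporting of severe symptoms, and Appendix A schedules an AE assessment, without an injection, at the Final Visit. The interval between the two is not stated, but 8.10 leaves scheduling detail to the MOP, which is not among the documents.
- *That 0 against 30 days is a difference in post-dose observation.* One period is counted from the Final Visit and the other from withdrawal. Neither is counted from the last dose, and 8.7 contradicts the 30 days.
- *That open events are formally closed without an outcome.* That is an inference from 12.4.2 with 11.1; the protocol does not say so.
- *That primary endpoint counts are lost wholesale.* An event open at the Final Visit has already been counted and graded, and 13.4.2 does not tabulate outcome.

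**Conclusion.** The contradiction is real on the text. Section 8.6 requires follow-up that 12.4.2, read with 11.1, ends at the same visit, and no other section restores it for completers. A moderate, severe or serious event open at a completer's Final Visit has no required follow-up or outcome, and worsening or new onset afterwards falls outside collection.

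The effect is limited. It bears on outcome, later change in grade and late onset, not on what has been recorded by the Final Visit. How many events would be affected cannot be estimated from the documents. The conclusion rests on taking the end of participation in 12.4.2 to be the completion defined in 11.1. If the sponsor means something else, the documents need to say so. Given that AEs are the primary endpoint, the point should be corrected, although it does not undermine the design.

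**What to change.** Reconcile 8.6, 8.7, 11.1, 12.4 and 12.4.2 so that completing the Final Visit does not end follow-up of events that 8.6 says require it, and so that 8.7 agrees with the 30 days in 12.4 and 12.4.2. Cite 12.4.2 in 8.6. How participants still symptomatic are managed clinically is for the sponsor to decide; the proposal here concerns data collection only.

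- Apply to completers the 30-day AE/SAE window that 12.4 already uses for withdrawals, counted from the Final Visit.
- Make one phone contact at the end of the window, with further contacts only for events still open.
- Obtain SAE outcomes for completers as 8.7 does for participants discontinued because of SAEs.

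The cost is amendment wording, one call for each of about 10–12 completers, and a few more calls for open events, since a single call cannot follow an event to resolution. Database lock moves by up to about 30 days after the last Final Visit, and longer only if an SAE outcome is pending.

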### **12.5 Reporting of Serious Adverse Events and Adverse Events**

#### **12.5.1 Reporting of Serious Adverse Events to DAIT/NIAID**

This section describes the responsibilities of the site investigator to report serious adverse events to the sponsor via the SAE CRF. Timely reporting of adverse events is required by 21 CFR and ICH E6 guidelines.

Site investigators will report to the SACCC (Rho, Inc.) and DAIT/NIAID all serious adverse events (see Section 12.2.4, Serious Adverse Event (SAE)), regardless of relationship or expectedness within 24 hours of discovering the event.

For serious adverse events, all requested information on the AE/SAE eCRF will be provided. However, unavailable details of the event will not delay submission of the known information. As additional details become available, the AE/SAE eCRF will be updated and submitted. Every time the SAE eCRF is submitted, it should be signed by the investigator.

For additional information regarding SAE reporting, contact Rho Product Safety:

Rho Product Safety  
[name]  
[name]  
Toll-free: [name]  
SAE Fax Line: [name]  
Email: [rho\\[contact]](mailto:[contact])

#### **12.5.2 Reporting to Health Authority**

This study will be conducted with an IND exemption; therefore no health authority reporting will be required. Annual and expedited reported, as described below, will be submitted to the DSMB and IRB, as appropriate.

##### **12.5.2.1 Annual Reporting**

DAIT/NIAID will include in the annual study report all adverse events classified as:

- Serious, expected, suspected adverse reactions (see Section 12.2.2, Suspected Adverse Reaction (SAR), and Section 12.2.3, Unexpected Adverse Event).
- Serious and not a suspected adverse reaction (see Section 12.2.2, Suspected Adverse Reaction (SAR)).

- Pregnancies not reported as serious adverse events.

Note that all adverse events (not just those requiring 24-hour reporting) will be reported annually.

#### 12.5.2.2 Expedited Safety Reporting

This option, with 2 possible categories, applies if the adverse event is classified as one of the following:

**Category 1: Serious and unexpected suspected adverse reaction [SUSAR]** (see Section 12.2.2, Suspected Adverse Reaction (SAR), and Section 12.2.3, Unexpected Adverse Event and 21 CFR 312.32(c)(1)i).

The sponsor must report any suspected adverse reaction that is both serious and unexpected. The DAIT/NIAID must report an adverse event as a suspected adverse reaction only if there is evidence to suggest a causal relationship between the study drug and the adverse event, such as:

1. A single occurrence of an event that is uncommon and known to be strongly associated with drug exposure (e.g., Grade 3 anaphylaxis as described in Table 12.3.2);
2. One or more occurrences of an event that is not commonly associated with drug exposure, but is otherwise uncommon in the population exposed to the drug (e.g., tendon rupture);
3. An aggregate analysis of specific events observed in a clinical trial (such as known consequences of the underlying disease or condition under investigation or other events that commonly occur in the study population independent of drug therapy) that indicates those events occur more frequently in the drug treatment group than in a concurrent or historical control group.

**Category 2: Any findings from studies that suggests a significant human risk**

The sponsor must report any findings from other epidemiological studies, analyses of adverse events within the current study or pooled analysis across clinical studies or animal or *in vitro* testing (e.g. mutagenicity, teratogenicity, carcinogenicity) that suggest a significant risk in humans exposed to the drug that would result in a safety-related change in the protocol, informed consent, investigator brochure or package insert or other aspects of the overall conduct of the study.

DAIT/NIAID must notify the DSMB, central IRB, and all participating investigators of expedited Safety Reports within 15 calendar days; unexpected fatal or immediately life-threatening suspected adverse reaction(s) shall be reported as soon as possible or within 7 calendar days.

#### 12.5.3 Reporting of Adverse Events to IRBs

All investigators will report adverse events, including expedited reports, in a timely fashion to their respective IRBs in accordance with applicable regulations and guidelines.

#### 12.6 Pregnancy Reporting

The investigator shall be informed immediately of any pregnancy in a study subject. A pregnant subject shall be instructed to stop taking study medication. The investigator shall counsel the subject and discuss the risks of continuing with the pregnancy and the possible effects on the fetus. Monitoring of the pregnant subject shall continue until the conclusion of the pregnancy.

The investigator shall report to the Statistical and Clinical Coordinating Center (SACCC) and DAIT/NIAID all pregnancies within 1 business day of becoming aware of the event using the Pregnancy eCRF. All pregnancies identified during the

study shall be followed to conclusion and the outcome of each must be reported. The Pregnancy eCRF shall be updated and submitted to the Statistical and Clinical Coordinating Center (SACCC) when details about the outcome are available.

Information requested about the delivery shall include:

- Gestational age at delivery
- Birth weight, length, and head circumference
- Gender
- Appearance, pulse, grimace, activity, and respiration (APGAR) score at 1 minute, 5 minutes, and 24 hours after birth, if available
- Any abnormalities.

Should the pregnancy result in a congenital abnormality or birth defect, an SAE must be submitted to the Statistical and Clinical Coordinating Center (SACCC) and DAIT/NIAID using the SAE reporting procedures described above.

### **12.7 Reporting of Other Safety Information**

An investigator shall promptly notify the site IRB as well as the SACCC and DAIT/NIAID via email when an “unanticipated problem involving risks to subjects or others” is identified, which is not otherwise reportable as an adverse event.

## **12.8 Review of Safety Information**

### **12.8.1 Medical Monitor Review**

The DAIT/NIAID Medical Monitor shall receive monthly reports from the SACCC compiling new and accumulating information on AEs, SAEs, and pregnancies recorded by the study site(s) on appropriate paper CRFs.

In addition, the Medical Monitor shall review and make decisions on the disposition of the SAE and pregnancy reports received by the SACCC (See Sections 12.5.1, Reporting of Serious Adverse Events to DAIT/NIAID and 12.6, Pregnancy Reporting).

### **12.8.2 DSMB Review**

The SACCC will provide the DSMB with listings of all SAEs on an ongoing basis, including quarterly reports of all SAEs. Furthermore, the DSMB will be informed of expedited reports of SAEs.

#### **12.8.2.1 Planned DSMB Reviews**

The NIAID Asthma and Allergy Data Safety and Monitoring Committee (DSMB) shall review safety data at least yearly during planned DSMB Data Review Meetings. Data for the planned safety reviews will include, at a minimum, a listing of all reported AEs and SAEs.

The DSMB will be informed of an Expedited Safety Report in a timely manner. An SAE which the Medical Monitor determines to be an unexpected safety risk will be sent to the DSMB immediately.

#### **12.8.2.2 Ad hoc DSMB Reviews**

In addition to the pre-scheduled data reviews and planned safety monitoring, the DSMB may be called upon for *ad hoc* reviews. The DSMB will review any event that potentially impacts safety at the request of the protocol chair or DAIT/NIAID. In addition, any occurrence of meeting one of the study stopping rules as described in Section 11.5 will

trigger an *ad hoc* comprehensive DSMB Safety Review. After review of the data, the DSMB will make recommendations regarding study conduct and/or continuation.

#### **12.8.2.3 Temporary Suspension of Enrollment and Drug Dosing for *ad hoc* DSMB Safety Review**

A temporary halt in both enrollment and drug dosing will be implemented if an *ad hoc* DSMB safety review is required.

### **13 Statistical Considerations and Analytical Plan**

#### **13.1 Overview**

The primary objective of this pilot study is to determine if treatment with this dose of mouse SCIT is safe. Other secondary objectives are to determine whether mouse SCIT will induce a 3-fold increase in mouse-specific IgE, a biomarker of allergen immunotherapy, when measured over 24 weeks, and to examine changes in levels of mouse-specific IgG and IgG4 over the same time period

#### **13.2 Endpoints**

##### **13.2.1 Primary Endpoints**

The primary endpoint is the number of reported adverse events and serious adverse events, including their severity, seriousness, and treatment relatedness.

##### **13.2.2 Secondary Endpoints**

1. Change in mouse-specific IgE.
2. Change in mouse-specific IgG and IgG4.
3. Change in in-vitro mouse antigen binding to B-cells.

#### **13.3 Measures to Minimize Bias**

This is a one arm open label study without randomization. All laboratory assays for serum IgE and IgG antibodies will be performed in a central laboratory.

#### **13.4 Analysis Plan**

##### **13.4.1 Analysis Population**

The study population consists of adults aged 18 through 55 years who have a history of asthma and are mouse sensitive. The study will examine the safety of the administration of non-standardized glycerinated mouse allergenic extract by subcutaneous injection. This is a phase I safety pilot with no efficacy measures; thus, only one analysis population, the safety population, will be defined for this study. The safety population will include all study participants who receive the initial injection during the Dose Initiation Visit. All statistical analyses will be performed on the Safety Population.

##### **13.4.2 Primary Analysis of Primary Endpoint(s)/Outcome(s)**

The primary objective of this pilot study is to assess if treatment with mouse SCIT, using the per protocol allergenic extract doses, is safe. This will be done by determining the rate of related adverse events and serious adverse events in the course of treatment. Frequency of AEs and SAEs will be tabulated by event, organ, seriousness, severity, and treatment relatedness.

##### **13.4.3 Analyses of Secondary Endpoints**

The secondary statistical analyses will include summary statistics for the secondary endpoints and correlation analyses. Endpoints that are proportions will be determined along with their exact 95% confidence intervals (Proc Freq, SAS).

Correlation analyses will test for associations between baseline allergy diagnoses (rhinitis, asthma), allergen sensitivity (mouse-specific IgE and IgG levels, skin test results), and increased risk of AEs. Changes from baseline levels of mouse-specific IgE, IgG, and IgG4 will be described in absolute and relative terms.

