## **2 Study Hypotheses/Objectives**

### **2.1 Hypotheses**

The two hypotheses tested by this study are 1) Subcutaneous treatment with mouse extract can be safely administered in adults with mouse sensitivity and 2) Subcutaneous treatment with mouse extract can induce significant changes in serum biomarkers indicative of immunologic activity.

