### 2.3 Secondary Objective(s)

1. To determine whether a 24 week treatment with mouse SCIT, using the per protocol allergenic extract doses, will induce a 3-fold increase in mouse-specific serum IgE.
2. To determine whether a 24 week treatment with mouse SCIT, using the per protocol allergenic extract doses, will induce changes in the serum levels of mouse-specific IgG and IgG4.
3. To determine whether a 24 week treatment with mouse SCIT, using the per protocol allergenic extract doses, will inhibit the in-vitro mouse antigen binding to B-cells.

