### 4.2 Participant Inclusion Criteria

Participants who meet all of the following criteria are eligible for enrollment. Participants may be reassessed if not initially eligible. Participants are eligible if they:

1. Are male or female adults, 18 through 55 years of age at recruitment.
2. Have a history of asthma for a minimum of 1 year before study entry.
  - i. A diagnosis of asthma will be defined as a report by the participant that they have had a clinical diagnosis of asthma made by a clinician over a year ago.
  - ii. The participant must have persistent asthma defined by the current need for at least 100 mcg of fluticasone per day or the equivalent of another inhaled corticosteroid.
  - iii. The participant's asthma must be well controlled as defined by:
    1. A FEV1 greater than or equal to 70% predicted with or without controller medication. (see Section 8.2).
    2. An Asthma Control Test (ACT) score  $\geq 20$ .
3. Are sensitive to mouse as documented by a positive ( $\geq 3$  mm greater than negative control) skin prick test result (using the same extract used for immunotherapy) and detectable mouse specific IgE ( $\geq 0.10$  kUA/L).
4. Have no known contraindications to therapy with glycerinated mouse allergenic extract.
5. Are willing to sign the written Informed Consent prior to initiation of any study procedure.

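### Section 13.4.3 does not say how a 3-fold IgE rise is judged, plans no interval or test for a continuous biomarker change, and correlates AE risk with asthma, which every participant has

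*Combined protocol and SAP*

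**What the plan says.** Objective 1, in the Synopsis and Section 2.3, is to determine whether treatment "will induce a 3-fold increase in mouse-specific serum IgE". Section 13.1 repeats it inside the statistical chapter: "will induce a 3-fold increase in mouse-specific IgE, a biomarker of allergen immunotherapy, when measured over 24 weeks". Section 2.1 lists, as the second of two hypotheses tested, "Subcutaneous treatment with mouse extract can induce significant changes in serum biomarkers indicative of immunologic activity".

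Section 13.2.2 gives the corresponding endpoint only as "Change in mouse-specific IgE", without a threshold.

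Section 13.4.3 is the only analysis text for secondary endpoints. It plans:

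- summary statistics and correlation analyses;
- for proportions, "Endpoints that are proportions will be determined along with their exact 95% confidence intervals";
- for the antibodies, "Changes from baseline levels of mouse-specific IgE, IgG, and IgG4 will be described in absolute and relative terms";
- for AE risk, "Correlation analyses will test for associations between baseline allergy diagnoses (rhinitis, asthma", followed by sensitivity measures (IgE, IgG, skin test).

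B-cell binding, secondary endpoint 3, is missing from the sentence on change and is covered only by the general mention of summary statistics. On eligibility, Section 4.2 requires of everyone: "Have a history of asthma for a minimum of 1 year before study entry". Section 13.4.1 describes the study population the same way.

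**The concern.** The objective and hypothesis ask yes/no questions, one of them with a numerical threshold. The analysis section gives neither a definition of the threshold nor a measure of uncertainty for the continuous change it describes. A 3-fold rise could be read as a geometric mean, an arithmetic mean, a median or a count of individual responders, and these need not agree. In an open-label study the choice could then be made after the results are known.

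Section 1.1 says the study is needed to supply immunogenicity as well as safety data before an efficacy trial, so a statement about 3-fold IgE is likely to be relied on. Separately, a factor that takes one value in every participant cannot be correlated with anything.

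**Working it through.** **The plan's own figure.** The only sizing figure is Table 13.6, the chance of at least one event in 280 injections: 1 − (1 − p)^280. At p = 1% this is 1 − 0.99^280 = 94.0%, as stated. The table concerns safety events; no figure is given for the IgE objective.

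**Inputs.** n = 10 (Section 13.6). The documents give no variability for IgE change, so I assume log-normal within-person ratios with SD of ln(ratio), s, from 0.5 to 1.2.

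**Uncertainty of a group ratio.** The 95% CI multiplies and divides the observed geometric mean ratio by exp(t × s/√n), with t(0.975, 9) = 2.262.

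| s | factor | CI around an observed ratio of 3 |
|---|---|---|
| 0.5 | exp(2.262 × 0.5/3.162) = 1.43 | 2.10–4.29 |
| 0.8 | 1.77 | 1.69–5.32 |
| 1.0 | 2.04 | 1.47–6.13 |
| 1.2 | exp(2.262 × 1.2/3.162) = 2.36 | 1.27–7.08 |

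**Uncertainty of a responder share.** Clopper–Pearson 95% limits: 5/10 gives 18.7%–81.3%; 8/10 gives 44.4%–97.5%.

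**Does the reading matter?** Suppose the true geometric mean ratio is exactly 3. With 10 participants:

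- observed geometric mean at least 3: 0.50, by symmetry;
- at least 5 of 10 participants with a 3-fold rise: P(Bin(10, 0.5) ≥ 5) = 0.62;
- lower 95% limit above 3: 0.025;
- lower 95% limit above 1, which shows a rise but not a 3-fold one: 0.87 at s = 1.0 (noncentral t, 9 df, noncentrality ln 3 × √10/1.0 = 3.47), 1.00 at s = 0.5 and 0.73 at s = 1.2.

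The first three do not depend on s.

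**Arithmetic against geometric mean.** In simulated studies of 10, the share in which the arithmetic mean ratio reaches 3 while the geometric mean does not, for s from 0.5 to 1.2, is 0%–37% at a true geometric mean ratio of 1.5, 3%–51% at 2, and 3%–20% at 4. The size of this disagreement thus depends on two assumptions, the SD and the true ratio.

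**Which participants count.** All analyses use everyone dosed (Section 13.4.1). Early stoppers give a final blood sample (Sections 6.5 and 8.6). Section 11.3 replaces withdrawals, while Section 6.5 limits replacement to early dropouts. Either way, the dosed group can exceed the group with a 24-week sample. Illustration: 12 dosed, 10 with a 24-week sample, 8 of those with a 3-fold rise. Among those sampled, 8/10 = 80% (44%–97.5%). Among all dosed, 8/12 = 67% (35%–90%) if neither early stopper shows the rise, or 10/12 = 83% (52%–98%) if both do in their last sample.

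**Asthma.** Code the diagnosis 1 for everyone. Its variance is 0, so its correlation with AEs is 0/0. Rhinitis, IgE, IgG and skin test results can vary and are not affected.

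**The case against.** The strongest reply is that this is a phase I safety pilot with no efficacy measures, sized on safety alone, for which description is appropriate. That stands: no power calculation or pass/fail test is needed for IgE. But objective 1 and hypothesis 2 are then worded beyond what the analysis delivers, and the wording can be changed.

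A second reply is that the plan already has the tools. Relative change is the fold-change scale, summary statistics may include a spread, and an exact interval is named for proportions. This also stands in part. A reader might infer that any 3-fold claim would rest on a bare point estimate; the documents do not support that, because a responder reading would bring the exact interval into play. What is missing is the sentence that adopts that reading, and an interval for the continuous change.

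A third reply is that the asthma term is a one-word slip that biases nothing. Agreed. A reader might infer that the whole set of correlations fails; only that term does.

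Finally, a reader might infer that the antibody baseline is undefined because Section 8.2 is headed as a combined screening and baseline visit. Section 8.4 and Appendix A, note 3, in effect place the antibody baseline at Dose Initiation, so one clarifying sentence is enough.

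**Conclusion.** The point holds. As written, Section 13.4.3 cannot answer objective 1 or hypothesis 2 as worded, and one listed correlation cannot be computed. The missing definition matters: at a true ratio of 3, the chance of declaring a 3-fold rise runs from 0.025 to 0.62 across three plausible readings, assuming log-normal ratios. The interval widths, 2.1–4.3 to 1.3–7.1 around an observed ratio of 3, rest on the assumed SD range of 0.5 to 1.2.

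The figure of up to 51% disagreement between arithmetic and geometric means should not be read as a property of this trial. It comes from one pairing of assumed SD and true ratio, and no section proposes an arithmetic mean. Nothing here touches the primary safety analysis, and the secondary aims remain reasonable as estimation.

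**What to change.** In Section 13.4.3:

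1. For IgE, IgG and IgG4, report the geometric mean within-person ratio of the 24-week sample to the Dose Initiation sample, with a 95% CI. Report the change in B-cell binding with a 95% CI. Call these estimates, unadjusted for multiplicity, and reword hypothesis 2 in Section 2.1 to match.
2. For objective 1, report the number and proportion of participants with at least a 3-fold IgE rise, with the exact 95% CI the plan already names. In the Synopsis and Sections 2.3 and 13.1, change the aim from determining whether to estimating.
3. State how many Safety Population participants lack a 24-week sample. Show the proportion among those who have one and, as a sensitivity analysis, the proportion in the full Safety Population using the final or early-stop sample where one exists. Give the number with no later sample separately.
4. Delete asthma from the correlation list, or replace it with a screening measure that varies, such as FEV1 % predicted or ACT score.
5. State that baseline for the antibody measures is the Dose Initiation draw. Leave the Section 8.2 heading as it is, since skin testing is done only at Screening and the only pre-treatment spirometry is there too.

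The cost is wording; the blood draws are already scheduled. The downside is that the intervals will be wide and unadjusted, so the report must not treat any one of them as confirmatory.
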